### 2.3 Overall Study Design

This is an open-label, multi-centre study in patients with PAH who are currently on stable treatment with at least one PAH medication. It is planned to evaluate the PK profile (24-hour profile and trough levels) and the safety, tolerability and efficacy of four different zamicastat doses. Each patient will start treatment with the lowest dose (50 mg zamicastat once daily) and the dose will be up-titrated to the individual **highest tolerated dose** (HTD) i.e. up to 200 mg zamicastat once daily.

A data safety monitoring board (DSMB) will periodically review the safety data and will issue a recommendation if the doses can be used as planned.

This study will consist of:

- A screening period, 5 to 12 days: visit V1
- Up to four dose finding periods, 14 days each:
  - o Dose A: visits A1, A2 and A3
  - o Dose B: visits B2 and B3
  - o Dose C: visits C2 and C3
  - o Dose D: visits D2 and D3
- Maintenance period, 42 days: visits MPV1, MPV2 and MPV3
- Follow-up period:
  - o Visit FU (down-titration): 14 days after MPV3 (only for patients taking 150 mg or 200 mg zamicastat who will not participate in the extension study)
  - o Visit FU: 14 days after last IMP intake

After confirmed eligibility, patients will initiate treatment with Dose A (50 mg zamicastat once daily) at visit A1 and will be treated with this dose level for 14 days. If Dose A was considered safe by the investigator, the patient will be up-titrated to Dose B (100 mg zamicastat once daily) at visit A3 and the patient will continue with this dosage for 14 days. Patients not tolerating Dose A have to be withdrawn from the study.

After a positive safety evaluation at visit B3, the patient will be up-titrated to Dose C (150 mg zamicastat once daily) and the patient will continue on this dose level for a further 14 days. If Dose C was tolerated by the patient, he/she will be up-titrated at visit C3 to Dose D (200 mg zamicastat once daily) where the patient will remain for 56 days (14 days dose finding period + 42 days maintenance period).

Patients not tolerating their next dose at any time during the 14-days dose finding period will come immediately to the site or call the investigator (unscheduled visit), unless intolerance was detected during a scheduled visit and the dose will be down-titrated to the patient's previous tolerated dose. Then they will continue this treatment for 42 days during the maintenance period.

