The dose which will be taken during the maintenance period will be considered as an individual HTD.

At the end of the maintenance period, the patient will have the opportunity to continue treatment in an extension study (BIA-51058-202), which is described in a separate protocol.

Patients not tolerating their individual HTD during the maintenance period have to be withdrawn from the study.

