## 2.5 Treatment

The study medication is zamicastat (BIA 5-1058). One tablet of the IMP contains 100 mg of zamicastat.

Each patient will start treatment with 50 mg zamicastat once daily (Dose A) at visit A1 and will be up-titrated step by step to the individual HTD i.e. up to 200 mg zamicastat once daily.

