**Table 1: Dosage regimen**

Daily dose	
Dose A	50 mg (half a tablet of 100 mg)
Dose B	100 mg (one tablet of 100 mg)
Dose C	150 mg (one and a half tablet of 100 mg)
Dose D	200 mg (two tablets of 100 mg)

Each next dose will start after 14 days of treatment if the previous dose was considered safe by the investigator. The up-titration is based on the following safety criteria, including but not limited to:

- Absence of symptomatic and/or clinically relevant orthostatic hypotension
- SBP > 95 mmHg or DBP > 50 mmHg
- Absence of clinically significant changes in ECG parameters (heart rate, P-R interval, QRS duration, QT and QTc interval)
- Absence of clinically significant hypersensitivity/skin allergic reactions

Patients not fulfilling the criteria for up-titration after 14 days of treatment with 50 mg zamicastat have to be withdrawn from the study.

If the patient's next dose will not be tolerated by the patient, the dose has to be down-titrated to his/her previous dose and this dose will be considered as the individual HTD, if tolerated by the patient. Treatment at the individual HTD will be for 42 days during the maintenance period.

Zamicastat has to be taken in the morning after breakfast. The patient must not take the tablet at home on visit days (A3/B3/C3/D3, MPV1, MPV2 and MPV3).

Patients taking 150 mg or 200 mg of zamicastat and who will not participate in the extension study will take 100 mg zamicastat for 14 days.

In case a patient will discontinue the study early due to the occurrence of an AE, down-titration is not mandatory, but at the investigator's discretion.

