### 4.3 Dose Group Names and Labels

Statistical output for baseline characteristics, as well as visit-based safety and efficacy evaluations, will be presented by dose groups. Patients will be allocated to a particular dose group based on their individual HTD, while patients that do not tolerate the 50 mg dose will be allocated to the “No HTD” group for analysis by HTD.

Adverse events and concomitant medications will be summarised based on the concurrent IMP dose, without allocating patients to separate dose groups. Details of assignment of concurrent IMP doses will be further described in the Sections 5.3 and 5.6.1.

The labels to be used in the tables, listings and figures are defined in the table below.

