#### Table 15.3.1.1 Overall Summary of TEAEs – Safety Set

An overview of TEAEs:

- TEAE
- Non-serious TEAE
- Serious TEAE
- TEAEs of special interest
- Related TEAE
- Related serious TEAE
- Mild TEAE
- Moderate TEAE
- Severe TEAE
- TEAE leading to down-titration
- TEAE leading to discontinuation
- Serious TEAE leading to discontinuation

- Related TEAE leading to discontinuation
- TEAE leading to death

will be displayed during the trial as well as the dose finding, maintenance, and down-titration periods by dose and overall for the patients in the safety set.

Table 15.3.1.2 Incidence of TEAEs – Safety Set

Table 15.3.1.3 Incidence of Serious TEAEs – Safety Set

Table 15.3.1.4 Incidence of TEAEs of Special Interest – Safety Set

Table 15.3.1.5 Incidence of Related TEAEs – Safety Set

Table 15.3.1.6 Incidence of Related Serious TEAEs – Safety Set

Table 15.3.1.7 Incidence of TEAEs Leading to Down-Titration – Safety Set

Table 15.3.1.8 Incidence of TEAEs Leading to Discontinuation – Safety Set

Table 15.3.1.9 Incidence of TEAEs Leading to Death – Safety Set

TEAEs occurring during the trial as well as the dose finding, maintenance, and down-titration periods will be summarised by concurrent dose and overall via the numbers of adverse events, as well as counts and percentages of patients having experienced adverse events during the dose finding and maintenance periods and overall. Percentages will be based on the number of patients in the safety set. Here and in the tables below the SOC and PTs within each SOC will be ordered by descending overall incidence.

In addition, the following will be provided summarised by SOC and PT for the safety set for each dose and overall:

Table 15.3.1.10 Incidence of TEAEs by Severity – Safety Set

Table 15.3.1.11 Incidence of TEAEs by Relationship to IMP – Safety Set

All adverse event data will be listed as follows:

Listing 16.2.4.1.1 Adverse Events: MedDRA Coding

Listing 16.2.4.1.2 Adverse Events: General – Enrolled Set

Listing 16.2.4.1.3 Non-Serious Adverse Events – Safety Set

Listing 16.2.4.1.4 Serious Adverse Events – Safety Set

Listing 16.2.4.1.5 TEAEs of Special Interest – Safety Set

Listing 16.2.4.1.6 AEs Leading to Discontinuation – Safety Set

Listing 16.2.4.1.7 AEs Leading to Death – Safety Set

All AEs will be displayed by patient including the PT of an AE, start and stop dates, duration and other characteristics of AEs.

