Table 15.3.2.1.1.2 Summary of Clinical Laboratory Tests: Haematology – Safety Set

Table 15.3.2.1.2.1 Summary of Clinical Laboratory Tests: Biochemistry by HTD – Safety Set

Table 15.3.2.1.2.2 Summary of Clinical Laboratory Tests: Biochemistry – Safety Set

Table 15.3.2.1.3.1 Summary of Clinical Laboratory Tests: Coagulation by HTD – Safety Set

Table 15.3.2.1.3.2 Summary of Clinical Laboratory Tests: Coagulation – Safety Set

The default summary statistics of clinical laboratory test results will be presented by HTD and overall at V1, A3/B3/C3/D3, MPV1, MPV3/EDV and FUV2. The absolute change from baseline will be presented as well.

Table 15.3.2.1.4 Summary of Clinical Laboratory Tests: Urinalysis – Safety Set

Number and percentage of patients will be displayed by HTD and overall at V1, A3/B3/C3/D3, MPV1, MPV3/EDV and FUV2. Percentage will be based on the number of patients at the specified visit.

Table 15.3.2.2.1 Clinical Laboratory Tests: Incidence of Haematology Abnormalities – Safety Set

Table 15.3.2.2.2 Clinical Laboratory Tests: Incidence of Biochemistry Abnormalities – Safety Set

Table 15.3.2.2.3 Clinical Laboratory Tests: Incidence of Coagulation Abnormalities – Safety Set

Number and percentage of patients for each laboratory parameter will be displayed by HTD and overall in Low, CS Low, Normal, High and CS High categories. Percentage will be based on the number of patients at specified visit.

Table 15.3.2.2.4 Clinical Laboratory Tests: Incidence of Urinalysis Abnormalities – Safety Set

Number and percentage of patients for each laboratory parameter will be displayed by HTD and overall in Normal, Abnormal and CS abnormal categories. Percentage will be based on the number of patients at specified visit.

Table 15.3.2.3.1 Clinical Laboratory Tests: Shift Table of Haematology Results – Safety Set

Table 15.3.2.3.2 Clinical Laboratory Tests: Shift Table of Biochemistry Results – Safety Set

Table 15.3.2.3.3 Clinical Laboratory Tests: Shift Table of Coagulation Results – Safety Set

Shift tables showing changes in the number and frequency of patients with respect to the normal range between baseline and MPV3/EDV will be provided.

Table 15.3.2.3.4 Clinical Laboratory Tests: Shift Table of Urinalysis Results – Safety Set

Shift tables showing changes in the number and frequency of patients in Normal, Abnormal and CS abnormal categories between baseline and MPV3/EDV will be provided.

Listing 16.2.4.2.1 Laboratory Data: Haematology – Enrolled Set

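### As written, by-dose TEAE percentages use the whole safety set as denominator, so patients never on a dose count as event-free at it

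*SAP*

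**What the plan says.** SAP 5.6.1 presents Tables 15.3.1.2 to 15.3.1.9 by concurrent dose and overall, for the whole trial and for the dose finding, maintenance and down-titration periods. The denominator is given once: "Percentages will be based on the number of patients in the safety set. Here and in the tables below the SOC and PTs". SAP 3.1 defines the safety set without reference to dose: one intake at any strength is enough. The numerator is dose-specific, because 5.6.1 assigns each event to the dose prescribed on its onset date.

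SAP 4.3 places patients in groups by highest tolerated dose (HTD) for visit-based tables, but treats adverse events differently: "Adverse events and concomitant medications will be summarised based on the concurrent IMP dose, without allocating patients to separate dose groups".

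Dosing is sequential and conditional. Under SAP 2.5 each patient starts at 50 mg and "will be up-titrated step by step to the individual HTD i.e. up to 200 mg zamicastat once daily", moving on only if the previous dose was judged safe. Patients who fail the criteria at 50 mg are withdrawn, and Protocol 9.4.2 does not replace withdrawals. For maintenance, SAP 2.3 says: "The dose which will be taken during the maintenance period will be considered as an individual HTD".

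Elsewhere the SAP names a narrower base. For laboratory tables, 5.6.2 says: "Percentage will be based on the number of patients at the specified visit".

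**The concern.** A percentage is interpretable as a risk at a dose only if its denominator is the set of patients who could have had an event at that dose. Here the numerator is limited to patients on the dose and the denominator is not. A patient withdrawn at 50 mg would be counted as event-free at 100, 150 and 200 mg.

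The second secondary objective is to describe how safe and well tolerated the different doses are. The planned adverse-event tables with a dose split all use concurrent dose; none by HTD is listed. If the programmed tables follow the text, differences between columns partly show how many patients were on each dose. A real rise in risk with dose could be flattened, or a false gradient created in either direction.

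**Working it through.** The plan states no TEAE percentage, so there is no figure to reproduce.

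**Inputs.** N = 32 is the planned number of patients (SAP 2.6), used here as the safety-set size. The number on dose d, n_d, is not in the documents and is assumed below. x_d is the number of patients with an event at dose d.

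**Formula.** Printed % = x_d / N. Incidence among exposed = x_d / n_d. Hence printed % = incidence among exposed × n_d / N.

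**Dilution factor n_d / N.** 32/32 = 1.00; 28/32 = 0.875; 24/32 = 0.75; 16/32 = 0.50; 8/32 = 0.25.

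**One affected patient.** The table prints 1/32 = 3.1% however many were exposed. Among exposed the figure is 1/3 = 33.3%, 1/8 = 12.5% or 1/16 = 6.3%.

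**Dose finding and whole trial.** Everyone starts at 50 mg, so the factor there is 1.00. Because escalation is stepwise and nobody is replaced, the factor can only stay level or fall at each higher dose. Doses taken in maintenance or down-titration were already taken in dose finding, so the whole-trial factors are the same.

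**Maintenance.** Each patient is on one dose, so the n_d add to at most N. The four factors add to at most 1 and average at most 0.25. A flat true incidence of 20% then prints as four figures adding to at most 20%, with a mean of at most 5.0%. The bound could be slightly exceeded if events on the down-titration day, which falls in maintenance, are credited to the higher dose.

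**Illustrations, flat 20% incidence at every dose.** The HTD splits are assumed. Each patient with an HTD below 200 mg is taken to have tried the next dose up. In the first row, exposed at 100 mg = 32 − 2 = 30, at 150 mg = 30 − 2 = 28, and at 200 mg = 28 − 3 = 25. Sample entries: 20% × 28/32 = 17.5%; 20% × 22/32 = 13.8%.

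| HTD 50/100/150/200 mg (no HTD) | Exposed in dose finding | Printed %, dose finding | Printed %, maintenance |
|---|---|---|---|
| 2/3/3/22 (2) | 32/30/28/25 | 20.0/18.8/17.5/15.6 | 1.3/1.9/1.9/13.8 |
| 22/3/3/2 (2) | 32/30/8/5 | 20.0/18.8/5.0/3.1 | 13.8/1.9/1.9/1.3 |
| 8/8/8/8 (0) | 32/32/24/16 | 20.0/20.0/15.0/10.0 | 5.0 throughout |
| 0/0/0/32 (0) | 32/32/32/32 | 20.0 throughout | 20.0 at 200 mg only |

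These are expected values; 20% of 2 or 3 patients is not an attainable count.

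**A masked rise.** Suppose 8 patients have an event at each dose and 32/28/24/16 are exposed. The table prints 8/32 = 25.0% at every dose. Among exposed the figures are 25.0, 28.6, 33.3 and 50.0%.

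**The case against.** The strongest reply is that the sentence is standard wording that names the population and leaves the column split understood. Similar wording governs tables by HTD: disposition (5.1.1), protocol deviations (5.1.2), and demographics and disease characteristics (5.2.1, 5.2.2). Read literally there, the sex percentages in one HTD column would be divided by all treated patients, which cannot be intended. The laboratory wording in 5.6.2 names the visit but not the HTD column, so it is loose too. The statement in 4.3 may mean only that a patient is not fixed to one dose. The shells are attached to the SAP (Section 10), and 4.1 promises a footnote giving each denominator.

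This makes a column-specific N a plausible intention, and it limits confidence in how the tables will be programmed. It does not supply the missing rule. For HTD tables, 4.3 creates groups whose size can serve as the column N; for adverse events it creates none. The phrase is also used literally in this SAP: Table 15.1.5.2, patients continuing by visit, makes sense only against the whole safety set. In 5.6.5, neighbouring ECG tables use the visit base and the safety-set base separately. A footnote discloses a denominator but does not choose one.

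It is also fair that the study is exploratory and that event numbers and patient counts are still printed, so no data are lost. The patients-by-visit table recovers exposure only approximately, because it can miss a patient who came off a dose before that dose's first scheduled visit.

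Finally, a corrected denominator would not make the columns fully comparable. Time at dose differs: 14 days at a dose passed through, against 200 mg, "where the patient will remain for 56 days (14 days dose finding period + 42 days maintenance period"). Patients down-titrated from 150 or 200 mg "who will not participate in the extension study will take 100 mg zamicastat for 14 days". Those who reach higher doses are also those who tolerated the lower ones. These limits remain after the fix and should be stated with the tables.

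**Conclusion.** The concern holds for the text as written. By-dose and by-period TEAE percentages are diluted by n exposed / N wherever not every safety-set patient was on that dose in that period. The 50 mg column for dose finding and for the whole trial, and the whole-trial overall column, are unaffected.

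The actual size and the direction of any false trend cannot be determined, because numbers per dose are not given. There is no bias if all patients reach 200 mg and stay on it. In maintenance, some dilution is unavoidable unless the whole safety set is on a single dose. The numerical examples rest on a safety set of 32 and on assumed splits.

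This should be fixed before the tables are produced. Confidence is medium: if the shells already use a column-specific N, only the SAP wording is at fault.

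**What to change.** In SAP 5.6.1 and the shells, define the denominator of each concurrent-dose column as the safety-set patients prescribed that dose with at least one intake while it was prescribed. For period splits, count intake within that period. This matches the numerator, which follows prescribed dose. Print the N in each column header and keep the full safety set for the whole-trial overall column. Apply the same rule to Tables 15.3.1.1, 15.3.1.10 and 15.3.1.11, which are also by dose but name no denominator of their own.

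So that no event falls outside its denominator, clarify the down-titration day. SAP 5.6.1 credits events starting that day to the previous dose, whereas SAP 2.5 uses that term for the lower one: "the dose has to be down-titrated to his/her previous dose and this dose will be considered as the individual HTD". The period definitions in 4.6 place the same day in maintenance. State which dose is meant for event assignment and reconcile these sections.

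The cost is SAP wording and table shells, with no new data collection. Prescribed dose and down-titration date are already recorded (5.4.2), as are on-site intakes and the last intake before each scheduled visit (5.4.1).

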## 5.6.2 Clinical Laboratory Evaluation

Clinical laboratory values for haematology, coagulation, biochemistry and urinalysis will be collected at screening (V1), visits A3/B3/C3/D3, MPV1, MPV3/EDV and FUV2 for each laboratory parameter.

Blood pregnancy test values will be collected only for women with childbearing potential at screening (V1) and urine pregnancy test will be collected at visits A1, A3/B3/C3/D3, MPV1, MPV2, MPV3/EDV and FUV2. For patients enrolled under protocol version final 1.0, urine pregnancy test will be evaluated at visits A1, A3/B3/C3/D3, MPV1, MPV2, MPV3/EDV.

The following parameters will be collected:

- **Haematology:** haemoglobin, haematocrit, red blood cell count (RBC), white blood cell count (WBC), differential - neutrophils, eosinophils, lymphocytes, monocytes and basophils, and platelet count.
- **Coagulation:** prothrombin time test (INR).
- **Biochemistry:** sodium, potassium, chloride, calcium, phosphate, blood urea nitrogen, aspartate transaminase (AST), alanine transaminase (ALT), gamma-glutamyl transferase (GGT), lactate dehydrogenase (LDH), alkaline phosphatase (ALP), creatine phosphokinase (CPK), creatinine, glucose, C-reactive protein, albumin, total protein, total cholesterol, low-density lipoprotein-cholesterol, high-density lipoprotein-cholesterol, triglycerides, and total bilirubin (bilirubin will be fractionated direct/indirect if elevated), haemoglobin A1c (HbA1c).

- **Urinalysis:** pH, specific gravity, protein, blood, glucose, ketones, bilirubin, urobilinogen, leucocytes and nitrites (local dipstick). Microscopy and other appropriate tests (as needed) will be performed if dipstick indicates any relevant abnormality.

Haematology, coagulation and biochemistry test results will be assigned an LNH classification according to whether the value is lower than (L), within (N) or higher than (H) the reference range for that parameter as provided by the corresponding laboratory.

For urinalysis shift tables, all parameters except pH and specific gravity will be assigned a “normal”/“abnormal” category based on the recorded result. “Negative” and “normal” results will be considered as normal, and any positive results will be considered as abnormal.

Clinical significance of laboratory values will be evaluated by the investigator.

The following statistical output will be provided:

Table 15.3.2.1.1.1 Summary of Clinical Laboratory Tests: Haematology by HTD– Safety Set

Table 15.3.2.1.1.2 Summary of Clinical Laboratory Tests: Haematology – Safety Set

Table 15.3.2.1.2.1 Summary of Clinical Laboratory Tests: Biochemistry by HTD – Safety Set

Table 15.3.2.1.2.2 Summary of Clinical Laboratory Tests: Biochemistry – Safety Set

Table 15.3.2.1.3.1 Summary of Clinical Laboratory Tests: Coagulation by HTD – Safety Set

Table 15.3.2.1.3.2 Summary of Clinical Laboratory Tests: Coagulation – Safety Set

The default summary statistics of clinical laboratory test results will be presented by HTD and overall at V1, A3/B3/C3/D3, MPV1, MPV3/EDV and FUV2. The absolute change from baseline will be presented as well.

Table 15.3.2.1.4 Summary of Clinical Laboratory Tests: Urinalysis – Safety Set

Number and percentage of patients will be displayed by HTD and overall at V1, A3/B3/C3/D3, MPV1, MPV3/EDV and FUV2. Percentage will be based on the number of patients at the specified visit.

Table 15.3.2.2.1 Clinical Laboratory Tests: Incidence of Haematology Abnormalities – Safety Set

Table 15.3.2.2.2 Clinical Laboratory Tests: Incidence of Biochemistry Abnormalities – Safety Set

Table 15.3.2.2.3 Clinical Laboratory Tests: Incidence of Coagulation Abnormalities – Safety Set

Number and percentage of patients for each laboratory parameter will be displayed by HTD and overall in Low, CS Low, Normal, High and CS High categories. Percentage will be based on the number of patients at specified visit.

Table 15.3.2.2.4 Clinical Laboratory Tests: Incidence of Urinalysis Abnormalities – Safety Set

Number and percentage of patients for each laboratory parameter will be displayed by HTD and overall in Normal, Abnormal and CS abnormal categories. Percentage will be based on the number of patients at specified visit.

Table 15.3.2.3.1 Clinical Laboratory Tests: Shift Table of Haematology Results – Safety Set

Table 15.3.2.3.2 Clinical Laboratory Tests: Shift Table of Biochemistry Results – Safety Set

Table 15.3.2.3.3 Clinical Laboratory Tests: Shift Table of Coagulation Results – Safety Set

Shift tables showing changes in the number and frequency of patients with respect to the normal range between baseline and MPV3/EDV will be provided.

Table 15.3.2.3.4 Clinical Laboratory Tests: Shift Table of Urinalysis Results – Safety Set

Shift tables showing changes in the number and frequency of patients in Normal, Abnormal and CS abnormal categories between baseline and MPV3/EDV will be provided.

Listing 16.2.4.2.1 Laboratory Data: Haematology – Enrolled Set

Listing 16.2.4.2.2 Laboratory Data: Biochemistry – Enrolled Set

Listing 16.2.4.2.3 Laboratory Data: Coagulation – Enrolled Set

Values of laboratory tests will be listed.

Listing 16.2.4.2.4 Laboratory Data: Urinalysis – Enrolled Set

All urinalysis (dipstick) data will be listed.

Listing 16.2.4.2.5 Laboratory Data: Microscopy – Enrolled Set

All microscopy data will be listed.

